5.2.7 Stable disease (SD): None of the above

5.3 TOXICITY CRITERIA

This study will utilize the CTCAE version 3.0 for all SAE reporting. A copy of the CTCAE version 3.0 can be downloaded from the CTEP home page (http://ctep.cancer.gov/protocolDevelopment/electronic_applications/ctc.htm). All appropriate treatment areas should have access to a copy of the CTC version 3.0.

6 STATISTICAL CONSIDERATIONS

6.1 PRIMARY ENDPOINT

The primary objective of this trial is to determine if the rate of minimal residual disease (MRD) identified in patients 6 months after beginning cladribine for treatment of HCL differs according to whether cladribine is combined with rituximab. Half of the randomized patients receive cladribine and rituximab concurrently, and all patients receive delayed rituximab at least 6 months after cladribine, if and when MRD is detected. Patients with blood-MRD at least 6 months after delayed rituximab may also receive a 2nd course of delayed rituximab if they did not receive rituximab simultaneous with cladribine. The most important secondary objectives are MRD-free

survival after cladribine, and MRD-free survival after delayed rituximab or after up to 2 courses of rituximab. MRD studies for the primary endpoint will be limited to 1) blood FACS, 2) bone marrow aspirate FACS and 3) BMBx IHC, so that patients will be considered MRD+ if any of these 3 tests is positive. Of these tests, only blood FACS will be used for triggering delayed rituximab, because it is the most sensitive test of MRD in blood and bone marrow results will be affected by compliance for the procedure. Blood and marrow RQ-PCR will also be studied but will not be used for the primary endpoint because RQ-PCR though extremely sensitive is too early in its development as an MRD study. All MRD studies except for RQ-PCR are performed in CLIA certified labs. If the patient has a non-HCL monoclonal population in the blood, including but not limited to monoclonal B-cell lymphocytosis (MBL) and monoclonal gammopathy of uncertain significance (MGUS), the blood or marrow PCR or RQ-PCR may be false-positive so these PCR tests are not evaluable for the primary endpoint.

Patients enrolled on this trial may have received 0 prior cycles of purine analog or 1 prior cycle of purine analog. Data from previous studies suggests that patients without prior purine analog exposure have a higher complete response rate when they receive cladribine (91%, with a median CR duration of 53 months) compared to those with 1 prior cycle of cladribine, who have a CR rate of 62% (along with 26% PRs) and an associated response duration of 23 months. As a result, since MRD and development of a complete response are inter-related, the levels of MRD found may quite possibly differ according to whether the patients have received previous cladribine or not. Patients will be assigned to cohorts (Cohorts 1 and 2) according to whether they have received prior purine analog or not. In addition, the study will be designed to have adequate numbers of subjects in each category (prior purine analog exposure or not) in order to ensure reasonable interpretation for each of the two strata.

The goal will be to randomize a total of 68 evaluable patients with 0 and 62 with 1 prior courses of purine analog at the time of starting cladribine on this trial. MRD evaluations will be performed every month for 3 months after treatment initiation, every 3 months for 2 years, and every 6 months thereafter. The evaluation made nearest to 6 months after cladribine will be considered the primary evaluation and may vary +/- 2 weeks (i.e. done at or 24-28 weeks) due to scheduling or drug administration. With 34 randomized patients in each arm of the group with no prior purine analog, there will be 80% power to detect a difference in MRD rates of 5% vs. 25% 6 months after cladribine with or without rituximab, respectively, a 20% difference, using a Fisher's exact test with a 0.1 one-sided significance level. With 31 randomized patients in each arm of the group with 1 prior course of purine analog, there will be 80% power to detect a difference in MRD rates of 10% vs. 35% 6 months after cladribine with or without rituximab, respectively, a 25% difference. Differences will also be explored using the other tests of MRD, including marrow and blood consensus PCR and RQ-PCR.

Because progression of HCL following exposure to cladribine on this trial is likely to be very slow, it is extremely unlikely that any patients will have progressed within 6 months of randomization to the point of needing treatment; thus, the comparison between patients' MRD outcomes at 6 months with and without rituximab is expected to be done without any bias. In the unlikely event that a patient does receive rituximab within that time frame, or if a rare patient is given rituximab prior to demonstration of MRD, the main analysis will be done using that patient as randomized, despite receiving rituximab prior to the 6 month evaluation. This is a standard intent to treat analysis.

6.2 SECONDARY ENDPOINTS

In addition to the primary goal of determining differences in the MRD level according to rituximab administration, the following goals will also be explored in patients on this study.

The most important secondary endpoints are MRD-free survival after cladribine, and MRD-free survival after up to 2 courses of rituximab. For the secondary endpoints of this protocol, and for triggering delayed rituximab, patients with or without CR are considered MRD+ if the blood FACS is positive or if low blood counts become inconsistent with CR (ANC < 1500/ μ l, Plt < 100,000/ μ l, or Hgb < 11). Patients FACS-negative in both blood and bone marrow aspirate are considered MRD-negative regardless of blood counts. Failure of cladribine and/or rituximab to clear MRD by blood FACS requires that this test be positive at 6 months since MRD at 1-3 months may clear by 6 months. However, MRD relapse will be considered when first detected, even if before 6 months, if cladribine and/or rituximab fail to clear MRD at 6 months. If simultaneous cladribine and rituximab is superior to cladribine and delayed rituximab, MRD-free survival after cladribine and after delayed rituximab should together be longer if cladribine was combined with rituximab than if used alone. In order to compare the probability of development of MRD as a function of time according to whether rituximab is used immediately or not, Kaplan-Meier curves for this endpoint will be created, beginning at the date of randomization, and compared using a two-tailed log-rank test. Patients who develop MRD will be considered to have had an event for the actuarial curve, while those without MRD found in this manner will be considered censored and will remain in follow-up for this endpoint. With each stratum considered separately, or if both strata are combined, the power for this comparison will potentially be low, but the results may demonstrate a trend if one is present. Measurement of best response to cladribine vs. cladribine + rituximab will also be done at 1 and 6 months after cladribine. The CR and PR rates will be reported, as well as appropriate 95% exact confidence intervals.

Other secondary endpoints include determining disease-free and overall survival, MRD rates after cladribine and rituximab separately and combined, correlation of MRD rates and tumor markers with clinical endpoints and determining whether cladribine + rituximab can lead to long-term freedom from relapse of MRD or CR/PR, using MRD/tumor marker data to determine when bone marrow biopsy can be avoided in managing HCL, determining if rituximab benefit is different in patients receiving their 1st or 2nd course of purine analog, prospectively evaluating the effect of cladribine and rituximab on normal T- and B-lymphocytes, and studying HCL biology using monoclonal immunoglobulin sequences. When possible, blood will be drawn to obtain RNA for microarray analysis. This will be particularly important in contrasting patients with HCL and HCLv. Finally, to correlate bone marrow MRI signal with bone marrow biopsy, patients will obtain cervical and thoracic spine MRI at baseline and at bone marrow restaging time points, when feasible.

These secondary goals will be determined using appropriate actuarial methods as needed, along with descriptive analyses. Other than the comparisons identified as being of primary interest (comparison of MRD 6 months after starting trial), all of these evaluations will be done with exploratory intent and reported without formal adjustment.

As mentioned in Section 1.3.12 above, the CD25-variant of HCLv has a much poorer prognosis after cladribine than classic HCL and would create a bias if such patients are randomized. Therefore, patients will be initially grouped based on having HCLv vs. HCL, and the HCLv patients will receive concurrent cladribine and rituximab. The first 68 HCL patients with no prior

purine analog and the 62 HCL patients with 1 prior courses of purine analog will be randomized. Based on data in the literature and data from prescreening LMB patients, out of 31 HCLv patients a historical CR rate 3% (1/31) and ORR of 35% (11/31) may be assumed from cladribine alone. If 20 patients are enrolled, and if there are 3 or more CRs in the 20 patients, there is only 7.5% probability this would occur if the true complete response rate were 5%; there is a 90.9% probability that this would occur if the true complete response rate were 25%. Thus, observing 3 or more CRs in 20 patients would provide strong evidence that the true complete response rate was consistent with 25% and more than 5%. If 20 patients are enrolled, and if there are 11 or more responses in the 20 patients, there is only 5.3% probability this would occur if the true response rate were 35%; there is an 87.8% probability that this would occur if the true response rate were 65%. Thus, observing 11 or more responses in 20 patients would provide strong evidence that the true response rate was consistent with 65% and more than 35%.

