- HCL with 0-1 prior courses of cladribine or pentostatin and treatment indicated.

Design:

- Cladribine 0.15 mg/Kg/day x5 doses each by 2hr i.v. infusion (days 1-5)
- Rituximab 375 mg/m²/week x8 weeks, randomize half to begin day 1, then repeat for all patients with blood-MRD relapse at least 6 months after cladribine. Also, may repeat for those with blood-MRD relapse at least 6 months after delayed rituximab.
- MRD tests used for the primary objective will be limited to BMBx IHC, blood FACS, and bone marrow aspirate FACS, all CLIA certified. Blood MRD relapse is defined as FACS positivity or low blood counts (ANC < 1500/ul, Plt < 100,000/ul, or Hgb < 11) attributed to HCL. Patients FACS-negative in both blood and bone marrow aspirate are considered MRD-negative complete response (CR) regardless of blood counts. Randomization: 68 HCL patients with 0 and 62 with 1 prior course of purine analog
- Statistics: 80% power to discriminate rates of MRD of 5 vs. 25%, or 10 vs. 35%

Abbreviated title: CdA plus/minus Rituxan for HCL

Version date: 09/21/2022

- Non-randomized HCLv arm: 20 patients with HCLv will begin rituximab with cladribine.
- Non-randomized HCL arm: 25 newly diagnosed patients will be enrolled to receive rituximab beginning day 1, but beginning before the 1st dose of cladribine, rather than after.
- Accrual ceiling: 175 evaluable patients (155 HCL and 20 HCLv)

TABLE OF CONTENTS

PRÉCIS.....	2
TABLE OF CONTENTS	4
STATEMENT OF COMPLIANCE	7
1 INTRODUCTION	7
1.1 Study Objectives	7
1.2 Background.....	8
1.3 Rationale	12
2 ELIGIBILITY ASSESSMENT AND ENROLLMENT	17
2.1 Eligibility Criteria.....	17
2.2 Screening Evaluation	19
2.3 Participant Registration and Status Update Procedures.....	20
2.4 Baseline evaluation	21
3 STUDY IMPLEMENTATION	22
3.1 Study Design.....	22
3.2 Drug Administration.....	24
3.3 Treatment Modifications	24
3.4 Protocol Evaluation	25
3.5 Concurrent Therapies.....	25
3.6 Radiation Therapy Guidelines	25
3.7 Cost and Compensation	26
3.8 Criteria for Removal from Protocol Therapy and Off Study Criteria	26
4 SUPPORTIVE CARE	27
4.1 Infections/Fever and Neutropenia.....	27
4.2 Blood product support	27
4.3 Cytokine Support.....	27
4.4 Tumor lysis syndrome	27
4.5 Infusion reactions.....	27
5 DATA COLLECTION AND EVALUATION	28
5.1 Data Collection	28
5.2 Response Criteria.....	29
5.3 Toxicity Criteria.....	30
6 STATISTICAL CONSIDERATIONS	30
6.1 Primary endpoint	30

6.2	Secondary endpoints	32
6.3	Additional Considerations	33

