3.1.3 Definition of MRD positivity

To determine MRD rates for the primary endpoint, incidence of MRD 6 months after cladribine, the following 3 CLIA-certified MRD tests will be used:

- Blood FACS
- Bone marrow aspirate FACS
- BMBx IHC
- For the primary endpoint, patients will be considered MRD+ if any of these 3 tests are positive. MRD relapse is defined as FACS positivity or low blood counts (ANC < 1500/uL, Plt < 100,000/uL, or Hgb < 11). Patients FACS-negative in both blood and bone marrow aspirate are considered MRD-negative regardless of blood counts. MRD in the BMBx by IHC is defined as a ratio of CD20+ cells to T cells of at least 1, and most of the CD20+ cells having morphology consistent with HCL. FACS uses multicolor flow cytometry to specifically identify and quantify HCL cells based on expression of CD19, CD22, CD20, CD11c, CD103, and restricted (lambda or kappa) light chains. Blood consensus PCR is reported as clonal rearrangement present (positive) or polyclonal rearrangement pattern present (negative). While MRD generally refers to HCL detected while a patient is in CR, patients with more than minimal disease in the BMBx, who by definition are not in CR, will also be considered MRD+ by IHC. Patients not in CR due to positive BMBx may be MRD-free by blood tests. Thus, blood MRD-free survival is usually shorter than, but could be equal to or longer than disease-free survival.

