5.2.3 Rules for response assessment

- No G-CSF or GM-CSF at least 4 weeks before major response.
- No transfusions at least 4 weeks before major response.
- Hgb requirement for major response may be dropped if iron stores are low (ferritin ≤ 20)
- Isolated low blood counts do not indicate relapse unless they are consistently low, i.e., at least 2 low counts > 1 week apart.
- A minimum duration of response is not required.

5.2.4 Complete remission (CR): All of the following:

- Absolute neutrophil count (ANC) $\geq 1500/\mu\text{l}$
- Platelets $\geq 100,000/\mu\text{l}$
- Hgb $\geq 11 \text{ g/dl}$
- Spleen non-palpable or not below costal margin on CT.
- Circulating HCL cells non-visible on Wright stain
- Lymph nodes $\leq 2 \text{ cm}$ (short axis)
- Absence of hairy cells on BM aspirate smears and bone marrow biopsy by H&E and Wright stains.
- CR with MRD in the BMBx by IHC is defined as CR and a ratio of B cells to T cells of at least 1, and most of the B cells having characteristics consistent with HCL.

- CR with MRD in the peripheral blood is defined as CR and a positive peripheral blood FACS or PCR.
- Patients meeting all criteria for CR except minimum levels of ANC, platelets and Hgb will be considered CR if MRD is absent by BMBx IHC and by flow cytometry of blood and bone marrow.

5.2.5 Partial Response (PR): All of the following:

- Neutrophils $\geq 1,500/\mu\text{L}$ or 50% improvement over baseline.
- Platelets $\geq 100,000/\mu\text{L}$ or 50% improvement over baseline.
- Hgb $\geq 11.0 \text{ g/dL}$ or 50% improvement over baseline. For patients who are transfusion-dependent at baseline, Hgb of $\geq 9.0 \text{ g/dL}$.
- $\geq 50\%$ decrease in circulating malignant HCL count from the pretreatment baseline.
- $\geq 50\%$ reduction in sum of products of perpendicular diameters or decrease to $\leq 2 \text{ cm}$ (short axis) in evaluable ($> 2\text{cm}$) lymphadenopathy.
- $\geq 50\%$ reduction in extent of spleen below costal margin by CT or physical exam, if abnormal at baseline.

5.2.6 Progressive disease (PD): Any of the following:

- $\geq 50\%$ increase in sum of products of perpendicular diameters of evaluable ($> 2\text{cm}$) lymphadenopathy or appearance of new evaluable lymph nodes $> 2 \text{ cm}$.
- $\geq 50\%$ increase in extent of spleen below costal margin by CT or physical exam, if abnormal at baseline.
- $\geq 50\%$ increase in the absolute number of circulating malignant lymphocytes.

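### Section 6.2 counts low blood counts as MRD relapse without the HCL attribution and repeat-count conditions given elsewhere, and the sections disagree on what triggers delayed rituximab (minor)

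*Combined protocol and SAP*

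**What the plan says.** **Event definition.** Section 6.2 introduces its rule with the words "For the secondary endpoints of this protocol, and for triggering delayed rituximab", and the rule is that "patients with or without CR are considered MRD+ if the blood FACS is positive or if low blood counts become inconsistent with CR". The thresholds are ANC below 1500/µl, platelets below 100,000/µl or Hgb below 11. There is one exemption: a patient whose FACS is negative in both blood and marrow aspirate is MRD-negative whatever the counts. A patient who develops MRD has an event on the Kaplan-Meier curve, and the arms are compared by a two-tailed log-rank test. Section 3.1.3 says "MRD relapse is defined as FACS positivity or low blood counts", with the same thresholds and exemption. Section 1.3.2 likewise accepts a positive blood FACS or cytopenias.

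**Conditions found elsewhere.** The précis ends the same list of thresholds with "or Hgb < 11) attributed to HCL". Section 5.2.3, under response assessment, says "Isolated low blood counts do not indicate relapse unless they are consistently low, i.e., at least 2 low counts > 1 week apart".

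**Retreatment trigger.** Section 3.2.2 gives delayed rituximab once blood FACS detects HCL. Section 6.1 says that, of the three MRD tests, blood FACS alone is used as the trigger. The précis gives rituximab on day 1 to half the randomized patients, "then repeat for all patients with blood-MRD relapse at least 6 months after cladribine", and its blood-MRD relapse includes HCL-attributed low counts. Sections 1.3.2 and 6.2 also let low counts trigger treatment.

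**The concern.** MRD-free survival after cladribine is one of the two endpoints that 6.2 ranks highest among the secondary ones. Section 1.3.2 explains why: a difference at 6 months would not by itself show that giving rituximab early is clinically better. The event should therefore be defined in one way. As the text stands, an analyst working from 6.2 and one working from the précis and 5.2.3 could assign different event dates to the same patient. Cytopenia without HCL is foreseeable, since section 1.2.6 lists late-onset neutropenia and prolonged pancytopenia among reports after rituximab.

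The trigger matters to patients as well as to the analysis. Rituximab is capped at 16 infusions, so a patient randomized to early rituximab has only one further course of 8. The sections should agree on when it is given.

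**Working it through.** The plan gives no event count, hazard ratio or power for MRD-free survival, so there is no figure to reproduce. The check sets the texts side by side and counts the scheduled tests.

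**1. Conditions on a count-based event**

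| Section | Attributed to HCL | Repeat low count | Exempt if FACS negative in blood and aspirate |
|---|---|---|---|
| Précis | yes | no | yes |
| 1.3.2 | no | no | yes |
| 3.1.3 | no | no | yes |
| 5.2.3 (response rules) | no | yes | not stated there |
| 6.2 | no | no | yes |

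Only the précis requires attribution, and only 5.2.3 requires confirmation. Section 6.2, which defines the analysis, has neither and cites neither.

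**2. A hypothetical case.** Blood FACS is negative at months 12 and 18. At month 15 one platelet count is 95,000/µl for a reason other than HCL, and it is normal when repeated. Under the précis this is not a relapse, because it is not attributed to HCL. Under 5.2.3 it is not a relapse, because it is isolated. Under 6.2 it is an event at month 15 unless the FACS exemption applies. Section 6.2 does not say how old the blood or aspirate result may be for that purpose.

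**3. Where counts stand alone.** Before month 6 the gap is small. Section 6.2 says that failure to clear MRD by blood FACS "requires that this test be positive at 6 months since MRD at 1-3 months may clear by 6 months", and the 6-month visit schedules blood FACS and marrow. After that, the calendar in 15.1.3 lists visits at 9, 12, 15, 18, 21, 24, 27 and 30 months, which is 8 visits.

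- CBC: all 8.
- Blood FACS: months 9, 12, 18, 24 and 30, so 5/8 = 62.5%.
- Marrow: months 18 and 30, so 2/8 = 25%.
- CBC without FACS: months 15, 21 and 27, so 3/8 = 37.5%.

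Section 6.1 instead schedules MRD evaluations every 3 months for 2 years and every 6 months thereafter. That puts an evaluation at months 15 and 21 and leaves month 27 alone: 1/8 = 12.5%. Example B in Appendix B scores an MRD recurrence at month 15, which fits 6.1 better than the calendar.

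**4. Which endpoint is exposed.** In Appendix B, examples B and E, MRD that appears before a delayed course does not end the MRD-free survival counted over the rituximab courses. The exposure is therefore mainly in initial MRD-free survival after cladribine.

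**5. Trigger.** Before delayed rituximab, 15.1.2 requires a new FACS if the last is more than 28 days old and a new marrow if there has been none for more than 6 months. If blood and aspirate are both FACS-negative, 6.2 does not trigger treatment and neither does 3.2.2. If blood is positive, both do. The texts part when counts are low, blood FACS is negative and the aspirate is not FACS-negative: 6.2 triggers rituximab and 3.2.2 does not.

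**The case against.** The best defence is that the sections should be read together. Section 5.2.3 is worded as a general statement about relapse, the test in 6.2 is whether counts have become inconsistent with CR, and the précis supplies attribution where it defines blood-MRD relapse. On that reading 6.2 is an abbreviation. This has force for the two-count rule, which is better called an uncited omission than a contradiction. It does not remove the problem: 6.2 covers patients with or without CR, does not point to 5.2.3, and 5.2.3 says nothing about attribution. Section 5.1.1 also lists MRD onset and relapse dates only for flow cytometry and biopsy IHC. That suggests count-based events may be few, but it does not override the definition in 6.2.

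On the trigger, 6.1 ranks only its three MRD tests and does not expressly rule out counts. That softens its conflict with 6.2, but the dosing rule in 3.2.2 still names blood FACS alone.

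A reader might infer more than the documents support:

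- *That the exemption is unusable at the 6 of 8 visits without marrow.* Section 6.2 does not require an aspirate from the same visit, and the work-up before retreatment can supply one.
- *That counts stand alone at 3 of 8 visits without qualification.* This holds on the 15.1.3 calendar but falls to 1 of 8 on the 6.1 schedule.
- *That an iron-deficient patient would be classified incoherently, because 5.2.3 says "Hgb requirement for major response may be dropped if iron stores are low" and 6.2 has no such waiver.* The protocol recognises CR with MRD as a category, and once the Hgb requirement is waived a low Hgb is arguably not inconsistent with CR.
- *That the arms are biased by a known amount or in a known direction.* Only one randomized arm receives rituximab at the start, so a difference is possible, but nothing in the documents gives its size or sign.

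**Conclusion.** The point stands as a minor one. Sections 6.2, 3.1.3 and 1.3.2 omit the attribution that the précis requires and neither state nor cite the confirmation in 5.2.3. Applied literally, 6.2 turns a single low count without HCL into an MRD event unless the FACS exemption applies. The trigger for delayed rituximab is also stated in two ways, with 3.2.2 and 6.1 on one side and 6.2, 1.3.2 and the précis on the other.

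Only the MRD-free-survival comparisons and the retreatment rule are affected. Section 6.2 calls the secondary evaluations exploratory and expects low power for this comparison. The primary endpoint uses blood FACS, aspirate FACS and biopsy IHC at 6 months, without counts, and is unaffected. The number of misclassified events cannot be estimated. The visit counts assume that the calendar table was extracted with its cells in the right columns.

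**What to change.** **Event.** In 6.2, 3.1.3 and 1.3.2, define the count-based event as ANC below 1500/µl, platelets below 100,000/µl or Hgb below 11 g/dl, attributed to HCL and confirmed by at least two low counts more than a week apart, dated at the first. Keep the exemption for negative FACS in both blood and aspirate. Add a sensitivity analysis in which only a positive blood FACS is an event. It answers the one small downside, that attribution is a judgement and no blinding is described.

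**Trigger.** State a single rule in the précis, 1.3.2, 3.2.2, 6.1 and 6.2. The simplest is a positive blood FACS, as 3.2.2 and 6.1 already have it. Under that rule, cytopenia from HCL with a negative blood FACS would not be retreated. If the team wants to treat it, both 3.2.2 and 6.1 need amending to add the same confirmed, HCL-attributed cytopenia; changing 3.2.2 alone would leave 6.1 out of step.

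**Cost.** Protocol and SAP wording, plus one sensitivity analysis on data already collected. No new tests or patients.

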1.1.2 Secondary Objectives

- To compare cladribine + rituximab vs. cladribine alone in terms of 1) initial MRD-free survival and disease-free survival, 2) response to delayed rituximab for relapse, to determine if early rituximab compromises later response, and 3) feasibility of administration as an outpatient by simultaneous rituximab beginning before the cladribine in nonrandomized HCL patients.
- To determine if MRD levels and tumor markers (soluble CD25 and CD22) after cladribine and/or rituximab correlate with response and clinical endpoints.
- To compare blood MRD-free survival in patients who receive cladribine and up to 2 courses of rituximab, with respect to whether the 1st course of rituximab was used simultaneous with cladribine.
- To determine, using MRD and tumor marker data, when bone marrow biopsy (BMBx) can be avoided in managing HCL.
- To compare response and MRD after the 1st and 2nd courses of cladribine.
- To evaluate the effects of cladribine and rituximab on normal T- and B-cells.
- To enhance the study of HCL biology by cloning, sequencing and characterizing monoclonal immunoglobulin rearrangements.

- To determine overall survival, particularly in patients with poor-prognosis HCL like HCLv.
- To correlate bone marrow MRI signal with bone marrow biopsy

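### Section 6.2 has no rule for death without MRD; read literally, its MRD-free survival curve censors deaths and overstates the chance of being alive and MRD-free

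*Combined protocol and SAP*

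**What the plan says.** Section 1.1.2 lists a comparison of the randomized arms on "initial MRD-free survival and disease-free survival". Section 6.2 gives the rank: "The most important secondary endpoints are MRD-free survival after cladribine, and MRD-free survival after up to 2 courses of rituximab". It then states what the curve is for: "In order to compare the probability of development of MRD as a function of time according to whether rituximab is used immediately or not". The curves are Kaplan-Meier, "beginning at the date of randomization", and are "compared using a two-tailed log-rank test".

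The event rule has two parts. First, "Patients who develop MRD will be considered to have had an event for the actuarial curve". Second, "while those without MRD found in this manner will be considered censored and will remain in follow-up for this endpoint".

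No third category exists. I found no other section that makes death an event in MRD-free survival or names a competing-risk method, and none of the six worked examples in Appendix B includes a death. Dates of death are collected for overall survival (Section 5.1.1). Overall survival and disease-free survival are listed in Section 6.2 as other secondary endpoints.

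**The concern.** An endpoint with survival in its name is normally read as the probability of being alive and free of the event. Under the two-part rule, a patient who dies MRD-negative falls into the censored group. The curve then treats that patient as someone who could still have been found MRD-positive later, with the same risk as the survivors.

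This matters for three reasons.

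- Section 1.3.2 says that a 6-month difference would not by itself show a better clinical outcome, and for that reason makes blood MRD-free survival the major secondary endpoint.
- Section 1.3.3 raises the possibility that giving the two drugs together increases infection risk. A fatal infection before MRD would not count against its arm in this curve or its log-rank test.
- Accrual is expected to take 15 years (Section 6.3.2) and follow-up is open-ended (Section 3.4.3), so deaths without MRD have time to accumulate.

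**Working it through.** **Plan's own figure.** There is none to reproduce. Section 6.2 gives no event count, hazard ratio, follow-up length or power for this endpoint. The randomized power figures in Section 6.1 belong to the 6-month Fisher's exact test. Exact enumeration gives 80.6% (34 per arm, 5% v 25%) and 80.3% (31 per arm, 10% v 35%) against the stated 80%. They do not depend on the censoring rule.

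**Direction, with no assumption about death rates.** At each time let n be the number at risk, m the new MRD events and d the deaths without MRD.

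- The planned curve multiplies factors 1 − m/n. The MRD-or-death curve multiplies 1 − (m + d)/n. The second factor is never larger, so the planned curve can never lie below the other. It lies above it once a death without MRD has occurred, as long as the planned curve is above zero.
- Each step in the cumulative incidence of MRD is (MRD-or-death curve just before) × m/n. Each step in one minus the planned curve is (planned curve just before) × m/n, which is at least as large. So the complement of the planned curve overstates the incidence of MRD once MRD events follow deaths.

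**Size of the overstatement.** Inputs, all assumed because the documents give no death rate: S = MRD-free proportion with deaths censored at a chosen time; D = proportion dying without MRD by that time, taken as independent of MRD.

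- Alive and MRD-free = S × (1 − D)
- Overstatement = S − S × (1 − D) = S × D

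Each cell shows alive and MRD-free, with the overstatement in points in brackets:

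| S | D = 2% | D = 5% | D = 10% | D = 20% |
|---|---|---|---|---|
| 40% | 39.2% (0.8) | 38.0% (2.0) | 36.0% (4.0) | 32.0% (8.0) |
| 60% | 58.8% (1.2) | 57.0% (3.0) | 54.0% (6.0) | 48.0% (12.0) |
| 70% | 68.6% (1.4) | 66.5% (3.5) | 63.0% (7.0) | 56.0% (14.0) |

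**Size for the incidence of MRD.** With constant hazards a for MRD and b for death, cumulative incidence = a/(a + b) × (1 − S × (1 − D)). For S = 60% and D = 10% at 5 years:

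- a = −ln(0.60)/5 = 0.1022 and b = −ln(0.90)/5 = 0.0211
- cumulative incidence = 0.829 × 0.46 = 38.1%, against 1 − S = 40.0%

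This gap is small.

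**One early death in arms of this size.** A death without MRD, before any other event, lowers the MRD-or-death curve by 1/34 = 2.9 points, 1/31 = 3.2 points, or 1/65 = 1.5 points with the strata combined (34 + 31 = 65 per arm). It lowers the planned curve by 0.

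**Effect on the test.** Simulation with 65 per arm and 4,000 runs: the same MRD hazard in both arms (60% MRD-free at 5 years), excess deaths in the first half year, two-sided 5% log-rank test.

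| Early deaths | Planned test rejects | MRD-or-death rejects |
|---|---|---|
| 2% v 2% | 5.0% | 5.0% |
| 10% v 2% | 5.0% | 10.9% |
| 20% v 2% | 5.4% | 36.3% |

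The planned test keeps its level because the MRD hazards are equal, which is what a cause-specific test should do. It does not register the deaths.

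**The case against.** The strongest defence is that the rule was written with living patients in mind. It never mentions death, and a dead patient cannot remain in follow-up, so this may be an omission and not a decision to censor deaths. That stands as to intent. It does not tell the analyst what to do with an MRD-negative death, and the two-part rule as written leaves only censoring.

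A second defence is that the stated aim is the probability of developing MRD. For that aim, a log-rank test with deaths censored is a standard cause-specific comparison. If death and MRD are independent, the curve also estimates a net probability, meaning the chance of staying MRD-free if nobody died. Both points are right. The points in the table are therefore the gap between two estimands. They become an error when the curve is read as its name suggests, and its complement is still not the incidence of MRD in a population where people die.

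A reader might go further and infer that fatal toxicity cannot count against either arm, or that it disappears from the comparison that decides standard care. The documents do not support this:

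- Overall survival is a separate secondary endpoint, and deaths count there. Disease-free survival is also listed separately.
- Section 6.2 also scores low blood counts as MRD unless FACS is negative in both blood and marrow aspirate, so some patients who die with cytopenia may already be events. The précis narrows this to low counts attributed to HCL.
- No section makes this log-rank test the decision rule. Section 1.3.2 describes one pattern of results that would argue against changing standard treatment. Section 6.2 concedes that "the power for this comparison will potentially be low" and treats everything outside the 6-month MRD comparison as exploratory.
- Section 1.3.3 raises infection risk without any figure for deaths. Nothing in the documents supports an imbalance as large as 20% v 2%, and at 10% v 2% the two tests differ only modestly.

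**Conclusion.** The concern holds as a gap in the event rule of a prominent secondary endpoint. Followed literally, Section 6.2 produces a time-to-MRD curve with deaths censored under the name MRD-free survival. That curve overstates the probability of being alive and MRD-free, and its complement overstates the cumulative incidence of MRD. A death without prior MRD does not count against its arm in this curve or its test.

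The direction is certain; the size is not. It rests on assumed death and MRD proportions and on independence between them: 2 to 8 points at 40% MRD-free, 3.5 to 14 points at 70%, with 5% to 20% deaths. If deaths are few (2% to 5% at 60% MRD-free) it is 1.2 to 3.0 points. The assumed levels are illustrations, not forecasts for this trial.

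The log-rank test is valid for the cause-specific MRD hazard, and the primary 6-month analysis and its power are unaffected. The plan should be corrected on this point, but its main result does not depend on it.

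**What to change.** In Section 6.2, state that death from any cause without prior MRD is an event in MRD-free survival, and that living patients without MRD are censored. Apply this both to the endpoint after cladribine and to the one after up to 2 courses of rituximab. An example with a death in Appendix B would settle the coding.

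If time to MRD is also wanted, report it under that name as cumulative incidence with death without MRD as a competing event, and keep the two-tailed log-rank test as a cause-specific comparison.

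The cost is a few sentences and a little more analysis. Dates of death are already collected, so no new visits, data or patients are needed. The MRD-free survival curves will look slightly less favourable.
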